4.5.3 Potential Drug Interactions

Potential Drug Interactions with Cabozantinib

Cytochrome P450: Data from a clinical drug interaction study (Study XL184-008) show that clinically relevant steady-state concentrations of cabozantinib appear to have no marked effect on the area under the plasma concentration-vs-time curve (AUC) of

co-administered rosiglitazone, a CYP2C8 substrate. Therefore, cabozantinib is not anticipated to markedly inhibit CYP2C8 in the clinic, and by inference, is not anticipated to markedly inhibit other CYP450 isozymes that have lower [I]/K_i values compared to CYP2C8 (i.e., CYP2C9, CYP2C19, CYP2D6, CYP1A2, and CYP3A4). In vitro data indicate that cabozantinib is unlikely to induce cytochrome P450 enzymes, except for possible induction of CYP1A1 at high cabozantinib concentrations (30 µM).

Cabozantinib is a CYP3A4 substrate and a weak substrate for CYP2C9 (but not a CYP2D6, CYP2C8, CYP2C19, CYP2B6, or CYP1A2 substrate), based on data from in vitro studies. Results from a clinical pharmacology study, XL184-006, showed that concurrent administration of cabozantinib with the strong CYP3A4 inducer, rifampin, resulted in an approximately 77% reduction in cabozantinib exposure (AUC values) after a single dose of cabozantinib in healthy volunteers. Chronic co-administration of cabozantinib with strong inducers of the CYP3A4 family (e.g., phenytoin, carbamazepine, rifampin, rifabutin, rifapentine, phenobarbital, and St. John's Wort) may significantly decrease cabozantinib concentrations. The chronic use of strong CYP3A4 inducers should be avoided. Other drugs that induce CYP3A4 should be used with caution because these drugs have the potential to decrease exposure (AUC) to cabozantinib. Selection of alternate concomitant medications with no or minimal CYP3A4 enzyme induction potential is recommended.

Results from a clinical pharmacology study, XL184-007, showed that concurrent administration of cabozantinib with the strong CYP3A4 inhibitor, ketoconazole, resulted in a 38% increase in the cabozantinib exposure (AUC values) after a single dose of cabozantinib in healthy volunteers. Co-administration of cabozantinib with strong inhibitors of the CYP3A4 family (e.g., boceprevir, conivaptan, posaconazole, ketoconazole, itraconazole, clarithromycin, atazanavir, indinavir, nefazodone, nelfinavir, saquinavir, ritonavir, lopinavir, telaprevir, telithromycin, and voriconazole) may increase cabozantinib concentrations. Grapefruit, star fruit and Seville oranges may also increase plasma concentrations of cabozantinib and should be avoided. Strong

CYP3A4 inhibitors should be avoided and other drugs that inhibit CYP3A4 should be used with caution because these drugs have the potential to increase exposure (AUC) to cabozantinib. Selection of alternate concomitant medications with no or minimal CYP3A4 enzyme inhibition potential is recommended.

Please refer to [Appendix C](#) for the drug interaction table lists of substrates, inducers, and inhibitors of selected CYP450 isozyme pathways.

Other Interactions: A case of a drug-drug interaction between cabozantinib and warfarin has been reported in the literature (Foxx-Lupo et al. 2016). However, a causal relationship to drug exposure for the drug-drug interaction case described above cannot be established. As a precaution, administration of warfarin at therapeutic doses is not allowed in subjects receiving cabozantinib.

In vitro data suggest that cabozantinib is unlikely to be a substrate for P-glycoprotein, but has the potential to inhibit the P-glycoprotein transport activity ($IC_{50}=7.0\ \mu M$) at high concentrations. Additional details related to these overall conclusions can be found in the investigator brochure.

Administration of the proton pump inhibitor (PPI) esomeprazole resulted in no clinically-relevant effect on cabozantinib plasma PK in healthy volunteers. Therefore, concomitant use of gastric pH modifying agents (i.e., PPIs, H_2 receptor antagonists, and antacids) is allowed in subjects administered cabozantinib.

Additional details regarding potential drug interactions with cabozantinib can be found in the investigator brochure.

Cabozantinib was shown to be a substrate of drug transporter MRP2 in an in vitro assay. Administration of MRP2 inhibitors to subjects may result in increases in cabozantinib plasma concentrations.

Food Effects: As food increases exposure levels of cabozantinib, subjects should fast (with the exception of water) for at least 2 h before taking their dose of cabozantinib. After the 2-hour fast, subjects are to take

cabozantinib with a full glass of water (minimum of 8 oz or 240 mL) with no more food intake for one hour post-dose.

5.4.4 Palliative Care

Palliative radiation and surgery are allowed on this study IF they are not being used to address a target lesion as defined in RECIST 1.1. Any subject who required palliative care to a target lesion should be removed from protocol treatment. If necessary, the following parameters should be used:

- **Palliative Radiation**: protocol treatment should be held 3 weeks before, during, and at least 2 weeks after palliative radiation and complete wound healing, if a wound is present. If treatment is not resumed within 3 weeks, the case will be reviewed by PI and DSMC to determine whether or not subject can restart treatment.
- **Palliative Surgery**: Protocol treatment should be held 3 weeks before and until complete wound healing. Complete healing following abdominal surgery and radiation therapy and/or resolution of intra abdominal abscess must be confirmed prior to initiating treatment with cabozantinib. If the treatment is not resumed within 3 weeks, the case will be reviewed by PI and DSMC to determine whether or not subject can restart treatment.

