2.0 OBJECTIVES & ENDPOINTS

2.1 Primary Objective & Endpoint

The primary objective is to determine the progression-free survival (defined as CR+PR+SD) assessed at 12 weeks (~3-months) for subjects in Cohort 1 (Leiomyosarcoma Arm) treated with cabozantinib and temozolomide as defined by RECIST 1.1. The endpoint will be the time from the start of treatment to the time of progression, with progression defined as changes in RECIST 1.1 defined imaging, progression in non-target lesions as defined by RECIST 1.1, unequivocal clinical deterioration, or death from any cause. PFS, the primary endpoint, will be assessed after the first 12 weeks of therapy.

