4.5.2 Prohibited or Restricted Therapy

The following therapies are prohibited until study treatment has been permanently discontinued:

- Any investigational agent or investigational medical device.
- Oral anticoagulation with coumarin agents (e.g., warfarin), direct thrombin inhibitors (e.g., dabigatran), direct factor Xa inhibitor betrixaban, platelet inhibitors (e.g., clopidogrel), and chronic use of aspirin above low dose levels for cardio-protection per local applicable guidelines), until 4 weeks after cabozantinib has been permanently discontinued.
- Any non-protocol systemic anticancer treatment (e.g., chemotherapy, immunotherapy, radionuclides, drugs or herbal products used specifically for the treatment of the cancer under investigation).

The following therapies should be avoided until study treatment has been permanently discontinued or until otherwise specified:

- Local anticancer treatment including palliative radiation, ablation, embolization, or surgery with impact on tumor lesions should not be performed until radiographic progression per RECIST 1.1 has been established.
- Erythropoietic stimulating agents (e.g., epoetin alfa and darbepoetin alfa) should not be used based on a report of increased risk of tumor

recurrence/progression associated with erythropoietin (Wright et al 2007).

- Concomitant medications that are known to prolong the QTc interval should be avoided in subjects who receive cabozantinib until they have permanently discontinued cabozantinib treatment (refer to <http://www.qtdrugs.org> for a list of drugs which have the potential to prolong the QTc interval).
- Chronic co-administration of cabozantinib with strong inducers of the CYP3A4 family (e.g., phenytoin, carbamazepine, rifampin, rifabutin, rifapentine, phenobarbital, and St. John's Wort) may significantly decrease cabozantinib concentrations and should be avoided. Selection of alternate concomitant medications with no or minimal CYP3A4 enzyme induction potential is recommended.

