4.6 Duration of Therapy

Subjects will continue on study treatment until progressive disease, unacceptable toxicity or subject withdrawal.

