6.3 Evaluable for Objective Response

All subjects enrolled in the study should be assessed for response to treatment, even if there are major protocol treatment deviations or subjects exhibit objective disease progression prior to the end of Cycle 1.

All conclusions should be based on all enrolled subjects. Sub analyses may then be performed on the basis of a subset of subjects, excluding those for whom major protocol deviations have been identified (e.g., early death due to other reasons, early discontinuation of treatment, treating an ineligible subject, major protocol violations, etc.). However, these sub analyses may not serve as the basis for drawing conclusions concerning treatment efficacy, and the reasons for excluding subjects from the analysis should be clearly reported. The 95% confidence intervals for response rate should also be provided.

All subjects who were enrolled on the trial should be included in the main analysis of the response rate. Thus, an incorrect treatment schedule or drug administration does not result in exclusion. However, if a subject is removed from treatment prior to their 12 week assessment for reasons other than disease progression or death, they will be considered non-evaluable for response if approved by the DSMC.

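### Sections 4.5.2 and 5.4.4 give conflicting instructions on palliating a non-target lesion before progression, and 6.3 can make a subject removed for target-lesion palliation before week 12 non-evaluable for response

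*Combined protocol and SAP*

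**What the plan says.** **Palliation of a non-target lesion.** Section 4.5.2 has two lists, one of prohibited therapies and one of therapies to avoid. The second contains: "Local anticancer treatment including palliative radiation, ablation, embolization, or surgery with impact on tumor lesions should not be performed until radiographic progression". It does not separate target from non-target lesions. Section 5.4.4, which sits within Section 4.5 despite its number, says: "Palliative radiation and surgery are allowed on this study IF they are not being used to address a target lesion". It sets hold periods before and after the procedure and provides for restart. Neither section cites the other. Section 4.6 adds: "Subjects will continue on study treatment until progressive disease, unacceptable toxicity or subject withdrawal".

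**Palliation of a target lesion.** Section 5.4.4: "Any subject who required palliative care to a target lesion should be removed from protocol treatment". Section 6.3 then covers subjects who come off treatment ahead of the week-12 scan for a cause that is neither death nor progression. Its rule for this group is that "they will be considered non-evaluable for response if approved by the DSMC". The same section states "All conclusions should be based on all enrolled subjects", and it names early discontinuation of treatment as a reason for exclusion only in sub-analyses that cannot support efficacy conclusions.

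**Primary endpoint.** Section 2.1 describes it as "progression-free survival (defined as CR+PR+SD) assessed at 12 weeks". Progression means RECIST progression (including non-target lesions), unequivocal clinical deterioration, or death. Needing palliation is not on that list. Section 10.1 requires at least 13 of 42 Cohort 1 subjects with documented PFS at 3 months. Section 10.3 promises the percentage progression-free at 3 months with a 95% confidence interval, directly after saying that PFS will be estimated by Kaplan-Meier.

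**The concern.** There are two separate problems.

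The first is operational. A site with a subject whose non-target metastasis becomes painful at week 5 finds both answers in the protocol: wait for progression (4.5.2), or hold, treat and restart (5.4.4). In a multicenter trial this invites different handling of the same situation.

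The second concerns the denominator. A target lesion that needs palliation before week 12 may well belong to a subject who is failing treatment, though the documents do not say so. If the reason for removal is recorded as palliation and not as progression, that subject meets the 6.3 condition and can leave the response denominator with DSMC approval. The primary endpoint is itself built from response categories, so the same status could be carried into the 12-week rate. In a single-arm trial read against a fixed 20%, losing possible failures from the denominator pushes the reported estimate upward. Section 10 has no rule for these subjects.

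**Working it through.** **Step 1. Can 4.5.2 and 5.4.4 both be followed?** Treatment stops at progression (4.6), so the restart in 5.4.4 can only apply to a subject who has not progressed. That is the period in which 4.5.2 says not to perform the procedure. For a non-target tumor lesion before progression, the two instructions differ. They agree only where the procedure does not affect a tumor lesion, which 4.5.2 does not cover.

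**Step 2. Does target-lesion palliation meet the 6.3 condition?** Removal is required by 5.4.4. Palliation is not a listed progression event (2.1, 6.5). If removal comes before the 12-week assessment and no progression or death is recorded, the condition is met. An investigator could call the case unequivocal clinical deterioration, which would count as progression, but nothing directs this.

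**Step 3. Reproduce the design.** Inputs from 10.1: stage 1 has 14 subjects, stopping at 3 or fewer; the total is 42, favorable at 13 or more; 20% against 39%. With X1 ~ Bin(14, p) and X2 ~ Bin(28, p):

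P(favorable) = Σ over x = 4 to 14 of P(X1 = x) · P(X2 ≥ 13 − x)

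- p = 0.20: 0.0478 (stated alpha 0.05)
- p = 0.39: 0.8010 (stated power 0.80)

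The plan's design is reproduced.

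**Step 4. Effect on the decision.** Section 4.9 replaces only subjects who received no dose. Section 4.4 adds replacement only for the safety run-in, within its 4-week observation period. Otherwise a dropped subject is not made up and cannot add to the 13. Assume 1, 2 or 3 stage-2 subjects of average risk are dropped, with cut-offs unchanged (n = 41, 40, 39). P(favorable) at p = 0.20 is then 0.0412, 0.0351 or 0.0295. It falls.

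**Step 5. Effect on the reported rate, as a simple proportion.** The counts are assumed because the documents give none. With 13 successes and k failures deleted, the rate is 13/(42 − k). Intervals are exact (Clopper-Pearson, also assumed).

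| k | Rate | 95% CI |
|---|---|---|
| 0 | 13/42 = 31.0% | 17.6% to 47.1% |
| 1 | 13/41 = 31.7% | 18.1% to 48.1% |
| 2 | 13/40 = 32.5% | 18.6% to 49.1% |
| 3 | 13/39 = 33.3% | 19.1% to 50.2% |

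If no subject is affected, nothing changes.

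**Step 6. Effect if 10.3 means a Kaplan-Meier estimate.** The subject is then not deleted but may be censored at removal. Take 13 subjects progression-free at 12 weeks, 28 observed failures, and one would-be failure censored after j of those failures. The estimate is (42 − j)/42 × 13/(41 − j).

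- j = 0: 13/41 = 31.7%
- j = 28: 14/42 = 33.3%

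The direction is the same as for deletion. For one subject the shift is at least as large, against 31.0% if the failure is counted.

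**Step 7. Non-target palliation.** Target growth, new lesions, unequivocal non-target progression, clinical deterioration and death all remain events. The open case is a subject whose only progression would have been in the treated lesion and who did not deteriorate. If an average of 1 in 42 true failures were scored progression-free for this reason, p = 0.20 + 1/42 and P(favorable) = 0.0992. At half that, p = 0.20 + 0.5/42, it is 0.0703.

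**The case against.** The other side has several sound points.

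- **4.5.2 is the softer list.** Its heading says these therapies should be avoided, and allows for exceptions specified elsewhere. Section 5.4.4 can be read as the specific rule that prevails. This weakens the conflict but does not remove it: the bullet itself says the procedure should not be performed, makes no exception for non-target lesions, and has no cross-reference.
- **6.3 concerns response.** Its heading and wording are about response, and the primary endpoint has its own section (6.5). The all-enrolled rule and the limit on sub-analyses both pull against exclusion. DSMC approval is required, and its members have no direct relationship with the study. So the reach to the 12-week rate is an inference through the CR+PR+SD definition in 2.1. The reach to the response rate is direct.
- **The decision rule is protected.** Section 10.1 needs 13 subjects with documented PFS. A reader might infer that excluding these subjects makes a favorable conclusion easier to reach. The documents do not support that: Step 4 shows the false-positive chance falling. It would rise only if evaluable subjects were made up to 14 and 42, which 4.9 does not provide for.
- **The 13/41-type figures assume a simple proportion with deletion.** Section 10.3 can be read as Kaplan-Meier, in which case censoring is the route (Step 6).
- **Palliation is not proof of failure.** It may treat symptoms present at baseline. Scoring these subjects as not progression-free is a conservative convention, and it has a power cost.

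A reader might also take 9.9% as the trial's likely false-positive rate. It is an assumed upper bound for a narrow case.

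**Conclusion.** Both parts hold, with limited consequence. Sections 4.5.2 and 5.4.4 give opposite instructions for a non-target lesion before progression. Section 6.3 can take a subject removed for target-lesion palliation before week 12 out of the reported response rate and, by inference, out of the 12-week rate, against its own all-enrolled rule.

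The size is unknown because no frequency is given. Under an assumed one to three dropped failures, the reported rate moves from 31.0% to between 31.7% and 33.3%, a shift of 0.8 to 2.4 percentage points (from the unrounded rates) within an interval about 30 points wide. The 13-of-42 decision is not made easier, and the design's stated error rates are correct. Severity is minor to moderate.

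**What to change.** 1. In the 4.5.2 bullet, add an exception for palliation of a non-target lesion as permitted in 5.4.4.
2. In 6.3 and 10.1, state that removal under 5.4.4 before week 12 is not a ground for non-evaluable status. The subject stays in the 14 or 42 and in the response denominator, and counts as not progression-free at 3 months. This also settles the handling if the 3-month figure is a Kaplan-Meier estimate: the subject is an event and is not censored at removal.
3. Optional: record the date and lesion of any non-target palliation before week 12, and report a sensitivity count scoring these subjects as not progression-free. The primary count is unchanged.

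A mandatory scan before each procedure is not needed.

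**Cost.** The change takes a few sentences and, with item 3, one extra data item. The reported rate may be slightly lower. Compared with an unreplaced non-evaluable subject, item 2 changes neither type I error nor power, since that subject could not add to the 13. If such subjects would otherwise have been scanned and scored progression-free, power falls from 80.1% to 76.3% at an assumed average of 0.5 of 42 (p = 0.39 − 0.5/42), or to 72.1% at 1 of 42 (p = 0.39 − 1/42).

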4.6 Duration of Therapy

Subjects will continue on study treatment until progressive disease, unacceptable toxicity or subject withdrawal.

4.7 Duration of Follow-up

Subjects with PD at the end of treatment will be followed every 6 months for 2 years (or until death) for survival. Subjects without PD at the end of treatment will be followed every 6 months for 5 years (or until death) for survival and progression. Patients will be followed by either clinic visits or phone call. Subjects who are removed from the study treatment for toxicity should be followed until toxicity resolved to grade 1 or baseline.

4.8 Removal of Subjects from Study Treatment and/or Study as a Whole

Subjects may discontinue study treatment or withdraw their consent to participate in the study at any time without prejudice. The investigator may withdraw a subject from study treatment or from the study if, in his or her clinical judgment, it is in the best interest of the subject or if the subject cannot comply with the protocol. The COH DCC and the Study PI should be promptly notified of the change in participant status.

In addition, any of the following conditions require discontinuation of the subject from study treatment:

- An AE or intercurrent illness that in the opinion of the investigator warrants the subject's withdrawal from study treatment;
- The investigator believes it is not in the best interest of the subject to continue on study;
- Specific conditions described in the Management of Adverse Events [Section 4.4](#);
- Necessity for treatment with other anticancer treatment prohibited by protocol;
- Sexually active subjects who refuse to use medically accepted barrier methods of contraception (e.g., male condom, female condom) during the course of the study and for 4 months after discontinuation of study treatment;
- Women who become pregnant or are breastfeeding;
- If the subject does not recover from his or her toxicities to tolerable Grade ≤ 2 within 6 weeks, the subject will have study treatment discontinued unless there is unequivocal evidence that the subject is benefitting. In this situation, a subject may be able to restart therapy with a dose reduction upon resolution of the toxicity and with agreement of the principal investigator /Sponsor;
- Request by regulatory agencies for termination of treatment of an individual subject or all subjects under the protocol;

- Significant noncompliance with the protocol schedule in the opinion of the investigator;
- Subjects who cannot tolerate the minimum protocol-specified dose of study treatment will have study treatment discontinued;
- Progressive disease (PD) or the subject no longer experiences clinical benefit as determined by the investigator;

4.9 Subject Replacement

If a subject is registered but withdraws or is taken off treatment before receiving any doses of study medication, he or she will then be replaced.

5.0 STUDY PROCEDURES TABLE

1. Screening assessments should be done within 28 days of first dose of study treatment (unless otherwise specified).
2. Cycle 1 Day 1 assessments should be done within 7 days of starting treatment. Pre-study procedures completed within 7 days of C1D1 do not need to be repeated. If a pre-study procedure was done more than 7 days prior to C1D1, then procedure needs to be repeated, but may be done within 5 days of starting therapy.

	Study Treatment Period			Post-Treatment Period
	Screening	Cycle 1 Day 1	C1D15, C2D1, C2D15, C3D1 and Day 1 of every following cycle (± 5 days)	30 Days after Last Dose/ Survival Follow-up
Informed Consent	X			
Demographics	X			
Medical and Cancer History/Demographics	X			
Physical Examination	X	X	X	X
Height	X			
Weight	X	X	X	X
Vital Signs	X	X	X	X
ECOG Performance Status	X	X	X	X
CBC with differential^a	X ^a	X	X	X
Chemistry Panel^a	X ^a	X	X	X
Urinalysis	X			X
Urine Protein/Urine Creatinine Ratio-UPCR^f	X ^f	X ^f	X ^f every 8 weeks	X
PT/INR, PTT^k	X ^k			
TFTs (TSH, FT3, FT4)^d	X		X ^d every other cycle	
12-lead ECG^c	X ^c		X ^c	
Cabozantinib Administration^j		X	X (daily)	
Temozolomide Administration^j		X	X (Days 1-5)	
Pregnancy Test^e	X	X	X ^e	X
QOL^h	X ^h	X ^h	X ^h	X
Correlative Blood Sampleⁱ		X ⁱ	X ⁱ	X ⁱ
Tumor Assessment^b	X		X ^b	
Concomitant Medications	X	X	X	X

NGS^m Report, if available	X			
Adverse Events	Continuous			X
Follow-up/Survival FU^g				X ^g

- a. Laboratory tests should include a standard hematology panel (CBC, differential, platelets) and chemistry panel (albumin, alkaline phosphatase, ALT, amylase, AST, bicarbonate, bilirubin, blood urea nitrogen, calcium, chloride, creatinine, γ -glutamyltransferase [GGT], glucose, lactate dehydrogenase, lipase, magnesium, phosphorus, potassium, sodium, total protein). Screening labs need to be done within 14 days of registration.
- b. All sites of known disease must be assessed. Radiology assessment by CT or MRI will be done at C2D15, C4D1, Cycle 6 and every 8 weeks (\pm 7 days) thereafter. After 1 year of protocol treatment, the scans can be obtained every 12 weeks (\pm 7 days) at the discretion of the subject and the treating physician.
- c. ECG: Performed during screening (within 28 days of first dose of treatment) and then **every 3 cycles** until end of treatment (\pm 5 days).
- d. Thyroid function tests (TSH, FT3, FT4) are performed during the screening period and then every 8 weeks (\pm 5 days). TSH is mandatory, FT3/FT4 are only required to be performed if TSH level is abnormal. Screening test should be done within 28 days of Cycle 1, Day 1.
- e. Pregnancy test: urine or serum at screening and on Day 1 of each cycle (\pm 5 days) for women of child-bearing potential.
- f. Urine protein/urine creatinine will be assessed during screening and **every 2 cycles** (\pm 5 days of D1 of the cycle) until the end of treatment. Screening UPCR should be done within 14 days of Cycle 1, Day 1 in which case Cycle 1, Day 1 assessment may be skipped.
- g. End of treatment visit will be completed within 30 days of the last dose of study drugs. Subjects with PD at end of treatment will be followed every 6 months for 2 years (or until death) for survival (from the last day of treatment). Subjects without PD at the end of treatment will be followed every 6 months for 5 year (or until death) for survival and progression (from the last day of treatment).
- h. The QOL questionnaires (EORTC QLQ-C30 and EuroQoL EQ-5D-3L) should be completed during screening, on Day 1 of every cycle prior to the study treatment administration, and at the end of treatment.
- i. Blood samples for mandatory correlative study will be collected at Cycle 1 Day1 prior to starting the treatment, and at C2D15, C4D1, and at the end of treatment (EOT) visit (\pm 5 days).
- j. Day 1 of each cycle should be every 28 days. In the event that this day falls on a holiday or other such event, study team should use \pm 5 days window to complete pre-treatment procedures, and dispense protocol agents to subjects with drug diaries and instructions to commence treatment on Day 1. Any missed doses will not be made up and should be skipped to maintain a 28-day cycle. Collection of drug diaries and drug accountability will be completed for the previous cycle on Day 1 of the following cycle.
- k. Screening PT/INR and PTT should be within 14 days of registration.
- l. Subjects with prior Next Generation Sequencing (NGS) reports completed on their tumor specimen will have this data collected.

*Once on treatment, if the subject is unable to have a study assessment taken within the defined time window due to an event outside of his or her control (e.g., clinic closure, personal emergency, inclement weather, vacation), the assessment should be performed as close as possible to the required schedule.

The Treatment Period ends when a subject receives his or her last dose of study treatment; the subject then enters the Post-Treatment Period.

